3. STUDY OBJECTIVE

The objective of this study is to demonstrate that the FRESCA Airbox Positive Airway Pressure System is non-inferior to the (predicate) FRESCA Positive Airway Pressure System.

[figure not shown]
4. STUDY DESIGN

4.1 General Study Design and Plan

This is a prospective, open-label, randomized, crossover assignment non-inferiority study conducted at up to 6 sites. Site participation is expected to be approximately 10 weeks from first subject enrollment until completion of the last study visit. After obtaining informed consent, subjects will attend a screening visit for inclusion/exclusion criteria evaluation.

Screening phase

- Collect informed consent
- Medical history/sleep history
- Weight, BMI, vitals
- Document medications
- Assess inclusion/exclusion criteria

FRESCA Medical Protocol: 18-01 Statistical Analysis Plan v1.0 (17JUN2019)

Schedule titration night and two additional sleep nights

Successfully screened subjects will undergo a PSG titration study using a standard CPAP device.

PSG Titration Night

- Perform PSG and adjust pressure to identify effective therapeutic pressure (i.e., AHI < 10).
- The PSG titration night will be scored by the study site's authorized personnel.

At the conclusion of a valid PSG titration night (i.e., ≥ 4 hours of sleep with no equipment recording failures and results in analyzable data for AHI and ODI), the subject will be assessed for proper fit to the FRESCA mask. The subject will breathe on the investigational flow generator and mask set to the titrated pressure for at least a 30-second interval to confirm proper mask fit.

Subjects who complete a valid PSG titration night and demonstrate proper FRESCA mask fit will be randomized to one of two sequences of in-lab PSG sleep nights, preferably on consecutive nights. The number of allowable calendar days between the two randomized sleep nights is 0-10 days.

Sequence 1 Subjects:

Night 1: Use of the predicate FRESCA device set to PAP at the PSG-titrated pressure.

Night 2: Use of the investigational FRESCA device set to Auto-Adjusting Pressure with EPR.

- a. The auto-adjusting pressure range will be set with the lower bound at 2 cmH₂O below the PSG-titrated pressure and the upper bound at 5 cmH₂O above the PSG-titrated pressure (not to exceed 20 cmH₂O).
- b. The EPR setting will be set to 3.

Sequence 2 Subjects:

Night 1: Use of the investigational FRESCA device set to Auto-Adjusting Pressure with EPR.

FRESCA Medical Protocol: 18-01 Statistical Analysis Plan v1.0 (17JUN2019)

- a. The auto-adjusting pressure range will be set with the lower bound at 2 cmH₂O below the PSG-titrated pressure and the upper bound at 5 cmH₂O above the PSG-titrated pressure (not to exceed 20 cmH₂O).
- b. The EPR setting will be set to 3.

Night 2: Use of the predicate FRESCA device set to PAP at the PSG-titrated pressure.

The study will employ a central scorer to score these two randomized PSG sleep nights. The central scorer will be blinded to the randomization sequence.

4.2 Randomization

Each subject will be assigned a sequential subject ID as they enter the screening visit. A subject is considered enrolled and eligible for randomization if they sign the informed consent document, meet all inclusion and exclusion criteria, complete a valid PSG titration study that identifies a therapeutic pressure setting (i.e., AHI < 10/hr.) and have a successful FRESCA mask fit. Treatment sequence assignments will be generated in a 1:1 ratio, using a block size of 4, for a subject to be randomized to either Sequence 1 (predicate FRESCA device on night 1 and investigational FRESCA device on night 2) or Sequence 2 (investigational FRESCA device on night 1 and predicate FRESCA device on night 2). Randomization will be managed within the electronic data management system that will

contain the assigned randomization number and treatment sequence assignment.

4.3 Study Assessments

Table I displays the Time and Events Schedule.

FRESCA Medical Protocol: 18-01

Statistical Analysis Plan v1.0 (17JUN2019)

Table 1: Schedule of Visits and Procedures

Visit	Screening Visit ≤45 days prior to PSG Titration	PSG Titration Night	Night 1	Night 2	Study Exit Visit ¹
1.12	Night	' 1 1 1.		•	
Informed Consent	Х				
Medical History	Х				
OSA History	Х				
Weight measure	Х				
Height measure	X				-
ВМІ	Х				
Vital Signs	Х		-		
Inclusion/Exclusion Review	х				
Confirm eligibility	Х	Х			
Schedule study nights	Х		4		
Medication Review	Х	Х	X	Х	
Randomization ²			Х		
PSG Procedure		Х	Х	X	
Sleep Scoring		Х	Х	Х	
Adverse Events		Х	Х	Х	Х

Study exit visit can be performed at the conclusion of the final sleep night.

5. PLANNED SAMPLE SIZE DETERMINATION

A sample size calculation was performed for the primary analysis of demonstrating non-inferiority of FRESCA Airbox treatment against the predicate (control) FRESCA treatment. It is planned to enroll up to 50 subjects across up to 6 study sites to yield at least 38 evaluable (mITT) subjects. Using 38 evaluable subjects for the primary analysis will provide 85% power to demonstrate non-inferiority assuming the mean difference between treatments is 0. These calculations also assume a 1-sided alpha level of 0.025%, standard deviation of 5 units, and a NI margin of 5 units. Sample size calculations were performed using the POWER procedure in SASv9.4, assuming a 2-group t-test between treatments, assuming a period effect in the ANOVA model as described in Section 10.1.

² Randomization can be performed upon completion of a successful Titration Night and subject enrollment.

◎쮋SIMULSTAT

FRESCA Medical
Protocol: 18-01
Statistical Analysis Plan v1.0 (17JUN2019)

6. STUDY ENDPOINTS

The primary efficacy measure in this study is AHI with mean AHI being the primary effectiveness endpoint. The difference in mean AHI between the new and predicate devices will be tested after treatment intervention in this cross-over study design. The secondary efficacy measure in this study is ODI with mean ODI being the secondary effectiveness endpoint,

Safety endpoints include procedure-related adverse events, device-related adverse events, serious adverse events (SAE), and unanticipated adverse device event (UADE).

7. ANALYSIS POPULATIONS

The intent-to-treat (ITT) population will include all subjects who are considered enrolled. The modified intent-to-treat (mITT) population will include ITT subjects with a Valid PSG Study during study nights 1 and 2.

8. GENERAL STATISTICAL CONSIDERATIONS

All analyses will be pooled across the enrolling sites, except otherwise stated, and conducted using SASv9.4 or higher. All baseline summary tables will include each sequence group and all subjects combined, while all effectiveness and safety table will include each treatment group. All listings will include all subjects in the ITT population.

Descriptive statistics will be used to summarize all endpoints. For continuous variables the descriptive statistics will include the number of subjects, mean, standard deviation, median, and range. The descriptive statistics for categorical variables will include the number of subjects and percent (%).

Formatting of numerical results will include the following:

- Mean values will be reported to 1 additional decimal place than collected.
- Standard deviation values will be reported to 2 additional decimal places than collected.
- Median and range values will be reported as the data are collected.
- Percentages will be reported to 1 decimal place.
- Confidence intervals will be reported to the same number of decimal places as the mean values.
- P-values being reported to 3 decimal places.

In-text tables will be brought in from post-text tables for the clinical study report.

注臘SIMULSTAT

FRESCA Medical Protocol: 18-01 Statistical Analysis Plan v1.0 (17JUN2019)

9. SUMMARY OF STUDY POPULATION DATA

9.1 Subject Disposition

Subject disposition will be summarized for all enrolled (ITT) and mITT populations. Numbers and percentages of subjects within each sequence group who completed each night and analysis populations will be displayed. In addition, reasons for withdrawal from the study will be included in this same summary.

A listing of subject disposition and analysis set inclusion will be provided and will include subject number, sequence group, inclusion in ITT population, inclusion in mITT population, outcome of study completion, and reason for withdrawal. An additional listing of protocol deviations will be provided, sorted by subject, and will include subject number, sequence group, deviation event, study night, deviation date, action taken, and if IRB reporting was required.

9.2 Demographics and Baseline Characteristics

Demographic and baseline characteristics will be summarized by sequence group for the mITT and PP populations. Two additional summaries will be provided, one each for demographics and baseline characteristics, providing descriptive statistics for subjects in the mITT population and subjects excluded from the mITT population. These two additional summaries will provide baseline demographic and baseline characteristics information for subjects completing Valid PSG nights (PSG Success) and subjects that did not complete a Valid PSG night.

Demographics to be summarized include:

- Age
- Gender
- Race
- Ethnicity

A listing of demographics will be provided and will include subject number, sequence group, age, gender, race, and ethnicity. The demographics of height, weight, and BMI will be included in the vital signs listing.

Baseline characteristics include:

FRESCA Medical
Protocol: 18-01
Statistical Analysis Plan v

Statistical Analysis Plan v1.0 (17JUN2019)

- AHI
- ODI
- AI
- SE (%)
- Minimum Sleep SpO₂ (%)
- Mean Sleep SpO₂ (%)
- Wakefulness (min)
- Stage N1 (min)
- Stage N2 (min)
- Stage N3 (min)
- REM (min)

A listing of the baseline characteristics will be provided in the PSG Data as described in Section 9.5.

9.3 Vital Signs

Vital signs collected at the baseline visit will be summarized descriptively by sequence group and include heart rate, diastolic blood pressure, systolic blood pressure, and oral temperature. A listing will be provided of vital signs collected at baseline and will include subject number, sequence group, oral temperature, heart rate, systolic/diastolic blood pressure, height, weight, and BMI.

9.4 Medical History

Medical history will be collected at baseline and a listing will be provided, sorted by subject, and will include subject number, sequence group, condition, start date, stop date, and if the condition is ongoing.

10. EFFICACY ANALYSES

The population for analysis for the primary outcomes is the mITT population. This population consists of the enrolled, intent-to-treat population who has evaluable data for both nights of PSG evaluation. Evaluable data includes nights that are considered valid PSG nights, defined as having at least 4 hours of recorded sleep time with no equipment (recording or therapeutic) failures and results in analyzable data for AHI and ODI values.

Mask settings, product information and malfunction measures will be summarized by sequence group and study night, with corresponding listings provided for each.

注IIISIMULSTAT

FRESCA Medical Protocol; 18-01 Statistical Analysis Plan v1.0 (17JUN2019)

A listing of PSG night parameters will be provided and will include subject number, sequence group, study night, AHI value, ODI value, arousal index (AI), sleep efficiency (SE %), Minimum Sleep SpO₂ (%), Mean Sleep SpO₂ (%), Wakefulness (min), Stage N1 (min), Stage N2 (min), Stage N3 (min), and REM (min).

10.1 Primary Efficacy Analysis

The primary endpoint in this study is mean AHI values. It is hypothesized that the new device treatment will be non-inferior to the predicate device treatment in mean AHI. The following 1-sided hypothesis will be tested for AHI:

H0: μ NEW - μ PREDICATE $\geq 0 + \Delta$ versus HA: μ NEW - μ PREDICATE $< 0 + \Delta$

Where μ NEW represents the mean AHI for the new device treatment, μ PREDICATE represents the mean AHI for the predicate device treatment, and Δ represents the non-inferiority margin. This analysis will assume a non-inferiority (NI) margin of 5 units and a 1-sided alpha level of 2.5%. A 2-sided 95% confidence interval (CI) will also be provided around the difference between treatments, where non-inferiority will also be demonstrated if the upper bound of the 95% CI is less than or equal to the NI margin of 5 units. In this scenario the 2-sided 95% CI equates to testing the 1-sided non-inferiority hypothesis.

The hypothesis will be tested using a t-test between treatments from an analysis of variance (ANOVA) model with treatment, sequence, and period as fixed effects and subject as a random effect. This model assumes no carry over effect.

The population for this primary endpoint analysis is the mITT population. The mITT population, by definition, will not have any missing data and hence, there will not be any imputation methods applied.

10.2 Sensitivity Analyses for Primary Endpoint

A sensitivity analysis will be conducted on the primary endpoint to assess a site effect.

This sensitivity analysis will be conducted in a similar manner as for the primary endpoint. The model described for the primary endpoint will also include a term for site

░龖SIMULSTAT

FRESCA Medical Protocol: 18-01

Statistical Analysis Plan v1.0 (17JUN2019)

in the ANOVA model. If the term for site is significant at the 2-sided alpha of 5% then it will be concluded that a site effect exists. Sites having less than 2 subjects in either treatment group will be pooled together into one site.

The primary analysis will also be conducted for the ITT population. There will be two sensitivity analyses using the ITT population, the first will use all ITT subjects and apply a multiple imputation method for missing AHI values. Missing values will be imputed based on baseline characteristics of sex, age, and baseline AHI value. The second sensitivity analysis will include all ITT subjects with observed data collected.

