11.4.2 Sensitivity Analyses for Primary Endpoint

A sensitivity analysis will be conducted on the primary endpoint to assess a site effect. This sensitivity analysis will be conducted in a similar manner as for the primary endpoint. The model described for the primary endpoint will also include a term for site in the ANOVA model. If the term for site is significant at the 2-sided alpha of 5% then it will be concluded that a site effect exists. Sites having less than 2 subjects in either treatment group will be pooled together into one site.

The primary analysis will also be conducted for the ITT population. There will be two sensitivity analyses using the ITT population, the first will use all ITT subjects and apply a multiple imputation method for missing AHI values. Missing values will be imputed based on baseline

characteristics of sex, age, and baseline AHI value. The second sensitivity analysis will include all ITT subjects with observed data collected.

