13. LIST OF TABLES

Table Number	Table Title	Analysis
Training!		Population
14.1.1	Subject Disposition by Randomized Sequence	IΠ
14.1.2	Subject Disposition by Randomized Sequence	mlTT
14.1.3	Demographics	mlTT
14.1.3.1	Demographics	Ш
	(mITT vs excluded mITT)	(mlTT vs non- mlTT)
14.1.4	Baseline Characteristics – PSG Data	mlTT
14.1.5	Baseline Vital Signs	mlTT
14.2.1	Primary Analysis (AHI)	mITT
14.2.1.1	Primary Analysis (AHI) – Site Effect	mitt
14.2.1.2	Primary Analysis (AHI) – Multiple Imputation	ITT
14.2.1.3	Primary Analysis (AHI) - Observed Cases	ITT
14.2.1,4	Primary Endpoint by Gender	mlTT
14.2.1.5	Primary Endpoint by BMI Category	miTT
14.2.1.6	Primary Endpoint by Site	mlTT
14.2.2	Secondary Efficacy Endpoint (ODI)	mlTT
14.2.3	Other PSG Paramters	mlTT
14.2.4	Device and Product Information – Night 1	ITT

SIMULSTAT

FRESCA Medical Protocol: 18-01

Statistical Analysis Plan v1.0 (17JUN2019)

14.2.5	Device and Product Information – Night 2	III
14.2.6	Device Malfunctions – Night 1	ITT
14.2.7	Device Malfunctions — Night 2	ITT
14.3.1	Procedure-Related Adverse Events	lπ
14,3,2	Device-Related Adverse Events	ITT

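### The ITT multiple imputation lists sex, age and baseline AHI but neither device nor the other night; pooled over devices, it shrinks the device difference toward zero

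*SAP*

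**What the plan says.** SAP 10.2 plans two ITT analyses of AHI beside the primary mITT analysis. In one, "the first will use all ITT subjects and apply a multiple imputation method for missing AHI values"; the rule given is "Missing values will be imputed based on baseline characteristics of sex, age, and baseline AHI value". Protocol 11.4.2 lists the same "characteristics of sex, age, and baseline AHI value". The other is an observed-case analysis: "The second sensitivity analysis will include all ITT subjects with observed data collected".

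The model to be fitted has "treatment, sequence, and period as fixed effects and subject as a random effect" (SAP 10.1). The imputed result has its own output, Table 14.2.1.2, "Primary Analysis (AHI) – Multiple Imputation" (SAP 13).

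Missing nights are allowed for in the planning: up to 50 subjects are enrolled "to yield at least 38 evaluable (mITT) subjects" (SAP 5). Under Protocol 10.6, an invalid PSG on either randomized night takes the subject out of the mITT analysis, so a subject may lack one night or both.

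Protocol 11.1 leaves further detail to the SAP, but the SAP adds none here. Neither document gives the imputation method, the data layout (one row per night or one per subject) or the number of imputations.

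**The concern.** Sex, age and baseline AHI are the same on a subject's two nights. An imputation model built on these alone cannot tell a new-device night from a predicate night, and it makes no use of an observed night in a subject who has one. The analysis model uses both pieces of information, so the listed imputation model is narrower than the model it feeds.

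Two programmers could follow the sentence and get different results:

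- **Pooled over devices.** Each missing night is drawn around a mean common to both devices, which pulls the estimated difference toward zero. If the new device is worse, this favours non-inferiority.
- **Separately by device.** The device effect is kept, but a night drawn without regard to the other night breaks the within-subject pairing and inflates the standard error.

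This table is meant to show whether leaving out incomplete subjects flattered the primary result. Under the pooled reading it would itself flatter a worse device.

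**Working it through.** **Inputs from the documents.** Up to 50 enrolled and at least 38 evaluable, SD 5, planned true difference 0 (SAP 5); margin 5 and one-sided alpha 2.5% (SAP 10.1). At full enrolment at most 50 − 38 = 12 subjects (24%) are incomplete.

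**Assumed, because the documents are silent.** Within-subject correlation 0.3 to 0.7; missing completely at random; baseline AHI explaining 5% of the variance (25% as a check).

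**Step 1, the plan's own figure.** A two-group t-test with 38/2 = 19 per group, SD 5 and margin 5 has noncentrality 5/(5·√(2/19)) = √9.5 = 3.08. Power at one-sided 2.5% is 85.1%, which reproduces the stated 85%. SD 5 is therefore taken as the SD of one night's AHI. SAP 5 prints alpha as 0.025%; at that level power would be 25.7%, so the 2.5% of SAP 10.1 is used.

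**Step 2, expected shrinkage under pooled imputation.** Set the predicate mean to 0 and the new-device mean to δ. Let m_N and m_P be the numbers of missing nights on each device among n = 50. Missing nights are drawn around the mean of all observed nights:

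c = δ(n − m_N)/(2n − m_N − m_P)

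Expected difference = [(n − m_N)δ + (m_N − m_P)c]/n

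With δ = 5 and 12 subjects incomplete:

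- A, new-device night missing in all 12: c = 190/88 = 2.16; (190 + 12 × 2.16)/50 = **4.32**
- B, both nights missing in all 12: 190/50 = **3.80**
- C, six missing on each device: 220/50 = **4.40**
- D, six missing both nights and six the new-device night: c = 190/82 = 2.32; (190 + 6 × 2.32)/50 = **4.08**

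The shrinkage is proportional to δ. At δ = 2.5 the mean is 0.76 × 2.5 = 1.9 (B) to 0.88 × 2.5 = 2.2 (C). At δ = 0 it is 0.

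**Step 3, simulation.** 3000 trials per scenario (Monte Carlo error about 0.3 points at 2.5%), 10 imputations, Rubin's rules with small-sample degrees of freedom, 2×2 crossover estimate; observed-case by REML with random subject. Results for true difference 5, 12 incomplete, correlation 0.5 (NI is the percentage of trials claiming non-inferiority; nominal 2.5%):

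| Pattern | Pooled mean | Pooled NI | By-device SE | By-device NI | Joint mean | Joint NI | Observed-case NI |
|---|---|---|---|---|---|---|---|
| A | 4.29 | 6.1 | +11% | 1.0 | 5.00 | 2.1 | 2.2 |
| B | 3.81 | 10.1 | +20% | 0.7 | 5.01 | 2.0 | 2.3 |
| C | 4.36 | 5.9 | +6% | 2.0 | 4.98 | 2.9 | 2.8 |
| D | 4.08 | 6.6 | +17% | 0.9 | 5.01 | 1.6 | 2.0 |

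Other settings:

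- Correlation 0.3: pooled NI 5.5% to 8.7%.
- Correlation 0.7: pooled NI 4.7% to 10.2%; by-device SE too large by 17% to 41%.
- Baseline AHI explaining 25% of variance, correlation 0.5: pooled NI 6.5% (A) and 12.3% (B).
- Fewer incomplete subjects, correlation 0.5: pooled NI 3.6% to 6.2% with 8 and 3.0% to 4.3% with 4.
- True difference 0, 12 incomplete, patterns A to C: pooled means 0.00 to 0.02; every method claims non-inferiority in 99.9% to 100% of trials.

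**Step 4, second simulation.** Patterns A to C were run again with correlation 0.3 and 0.6 and baseline AHI explaining 20% of between-subject variance (500 trials per scenario, Monte Carlo error about 0.7 points). Pooled means were 3.82 to 4.41 with NI 5.2% to 10.0%. Imputing by device plus the other night gave means of 5.00 to 5.08 and NI 1.2% to 3.4%. In pattern B at correlation 0.6 the mean distance from estimate to upper limit was 5.85 − 3.82 = 2.03 pooled, against 6.61 − 5.04 = 1.57 with device and other night. That wider interval partly offsets the bias, which is why the error rate does not rise further.

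**The case against.** The strongest reply is that the documents never say nights are pooled over devices. The sentence lists baseline characteristics, and device and other-night AHI are not baseline variables, so their absence need not mean exclusion. Of the layouts the text allows, one is biased, one is unbiased but conservative, and a joint model would be sound. No success rule attaches to this table; the primary mITT analysis uses no imputation, and the observed-case ITT analysis is a planned check that performs well. The largest figures need a true difference at the margin and all 12 possible losses, and 12.3% arises only when all 12 lack both nights and baseline AHI explains 25% of the variance. Imputing by device alone would remove the bias.

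Most of this stands, and it limits the consequence. The percentages describe how often one supportive table would cross the margin; they are not the trial's error rate. Twelve is a planning maximum, not a predicted dropout. The defect is an ambiguity with one harmful reading.

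It does not remove the point. No other section supplies the missing terms, and both ways of running the listed predictors do worse than a joint model that costs nothing extra. The observed-case table does not settle the matter either. Near the margin with 12 incomplete, the two ITT tables would differ by about 5 − 4.4 = 0.6 to 5 − 3.8 = 1.2/h on average from the imputation model alone, and a reader could mistake that for an effect of missing data.

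**Conclusion.** The concern holds, conditionally on how the listed predictors are used. Pooled over devices, Table 14.2.1.2 is biased toward non-inferiority in proportion to the true difference. At a true difference of 5/h with 12 of 50 incomplete, the mean estimate is 3.8 to 4.4/h and false non-inferiority 4.7% to 12.3% instead of 2.5%; with 4 incomplete the excess is small. By device without the other night, the analysis is unbiased but conservative. These figures rest on data missing completely at random, per-night SD 5 and correlation 0.3 to 0.7; the closed-form shrinkage does not depend on the SD or the correlation.

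The primary conclusion is not at risk. This should be corrected before database lock because it affects a prespecified supportive analysis. Confidence is medium because the intended layout is unstated.

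**What to change.** State in Protocol 11.4.2 and SAP 10.2 that AHI on the two devices is imputed jointly: one row per subject with a separate AHI variable for each device, each conditioned on the other, and sequence/period, sex, age and baseline AHI as predictors. Give the imputation method and the number of imputations in the same place.

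The cost is about one sentence in each document and a few lines of program. No new data are needed, and the primary analysis does not change.
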